9.9.2 Sample Size and Power Calculations for Efficacy Analyses (Secondary Objective)

The secondary endpoint associated with a hypothesis of this study is the percentage of participants developing COVID-19 through Day 14, regardless of SARS-CoV-2 results in baseline NP swabs. The related analysis population will consist of participants in the mITT population (see Section 9.5.1), approximately 1376 participants.

The power and sample size calculation for the secondary objective were computed using EAST and based on the following assumptions in addition to the assumptions listed in the previous section:

- The percentage of participants with detectable SARS-CoV-2 in baseline NP swabs is assumed to be 20% among the 1376 participants (see Section 4.2.3), resulting in approximately 276 participants with detectable SARS-CoV-2 in baseline NP swabs.
- The background secondary attack rate, in the absence of MOV, for participants with detectable SARS-CoV-2 in baseline NP swabs, is assumed to be ~40% based on the secondary attack rate calculated for the virus-positive participants in the REGEN-COV[™] prophylaxis study [O'Brien, M. P., et al 2021] [Food and Drug Administration 2021].
- The secondary attack rate for participants in the MOV group with detectable SARS-CoV-2 in baseline NP swabs is ~28% (with a risk reduction of 30% relative to the placebo group based on the reduction observed with REGEN-COV[™] in this population)
 [O'Brien, M. P., et al 2021] [Food and Drug Administration 2021].

Since the SARS-CoV-2 viral status at baseline will not be available before randomization, there is a potential imbalance in the 2 study intervention groups for participants with undetectable and detectable SARS-CoV-2 in baseline NP swabs. This also leads to different potential allocation ratios of participants with undetectable versus detectable SARS-CoV-2 in baseline NP swabs in the 2 study intervention groups. Assessment of power for this comparison is presented under 3 selected scenarios in Table 8:

 Scenario with more participants with detectable SARS-CoV-2 in baseline NP swabs in the MOV group (as listed in Table 7). There are approximately 188 participants with detectable SARS-CoV-2 in baseline NP swabs and 500 participants with undetectable SARS-CoV-2 in baseline NP swabs randomized to the MOV group. Approximately 88

participants with detectable SARS-CoV-2 in baseline NP swabs and 600 participants with undetectable SARS-CoV-2 in baseline NP swabs are randomized to the placebo group.

- Equal allocation scenario: There are approximately 138 participants with detectable SARS-CoV-2 in baseline NP swabs and 550 participants with undetectable SARS-CoV-2 in baseline NP swabs randomized to in each of the 2 intervention groups.
- Scenario with more participants with detectable SARS-CoV-2 in baseline NP swabs in the placebo group (as listed in Table 7 and described in Section 9.7). There are approximately 28 participants with detectable SARS-CoV-2 in baseline NP swabs and 660 participants with undetectable SARS-CoV-2 in baseline NP swabs randomized to the MOV group. Approximately 248 participants with detectable SARS-CoV-2 in baseline NP swabs and 440 participants with undetectable SARS-CoV-2 in baseline NP swabs are randomized to the placebo group.

All scenarios below are based on a total sample size of 1376 participants and an overall onesided, 2.5% alpha-level.

Sample Size	V-		V+		Total		
	MOV	Placebo	MOV	Placebo	MOV	Placebo	Power (%)
1376	500	600	188	88	688	688	24
1376	550	550	138	138	688	688	95
1376	660	440	28	248	688	688	>99

Table 8Power Analysis to Assess the Secondary Objective Participants; N=1376 OverallAlpha=0.025, One-Sided

baseline NP swabs

As shown in Table 8, the power for the secondary objective analysis is greater than 90% in second and third scenarios, given the stated assumptions. There is substantially less power in the first scenario where there is a marked and unfavorable imbalance in randomization of the participants with detectable SARS-CoV-2 in NP swabs, causing the difference in the overall secondary attack rates between the 2 intervention groups to be smaller.

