9.8 Multiplicity

Two main objectives will be evaluated in this study. A gatekeeping procedure that controls the overall FWER associated with the primary and secondary analyses will be used. The primary hypothesis (H1) is that MOV is superior to placebo for the prevention of laboratoryconfirmed COVID-19 in participants with undetectable SARS-CoV-2 in baseline NP swabs through Day 14. As stated in Section 9.6.1, the null hypothesis $p_t \ge p_c$ will be tested versus the alternative hypothesis $p_t < p_c$. The secondary hypothesis (H2) is that MOV is superior to placebo for the prevention of laboratory-confirmed COVID-19 in participants regardless of SARS-CoV-2 results in baseline NP swabs through Day 14. As stated in Section 9.6.1, this will be evaluated by testing the null hypothesis $p_{ts} \ge p_{cs}$ versus the alternative hypothesis $p_{ts} < p_{cs}$ pcs.

MK-4482-013-05 FINAL PROTOCOL

99

As stated in Section 9.7, although there is no plan to stop the study early for efficacy, a small statistical penalty (α =0.0001) will be applied for this interim analysis using a Haybittle-Peto type adjustment [Haybittle, J. L. 1971] [Peto, R, et al 1976]. The final analysis will be conducted at a 0.0249 alpha-level to preserve the overall type I error level.

Testing begins with the primary hypothesis (H1). The secondary hypothesis (H2) will be tested only if H1 is rejected. Both tests will be performed at the same one-sided 2.49% alpha-level. If H1 fails to reach statistical significance, then H2 will not be tested. In this way, the overall one-sided 2.5% type I error rate is controlled.

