9.9 Sample Size and Power Calculations

9.9.1 Sample Size and Power Calculations for Efficacy Analyses (Primary Objective)

The study will enroll approximately 1376 participants (regardless of SARS-CoV-2 results in baseline NP swabs) in a 1:1 ratio to MOV and placebo groups. Assuming approximately 80% of the 1376 participants will have undetectable SARS-CoV-2 at baseline (see Section 4.2.3), approximately 1100 participants will have undetectable SARS-CoV-2 at baseline and 276 participants will have detectable SARS-CoV-2 at baseline.

The primary endpoint of this study is the percentage of participants with undetectable SARS-CoV-2 in baseline NP swabs developing COVID-19 through Day 14. Thus, the primary analysis population consists of the approximately 1100 participants with undetectable SARS-CoV-2 at baseline, which is a subset of the 1376 participants randomized that is based on a factor (SARS-CoV-2 results in baseline NP swabs) that will not be available before randomization.

Moreover, because this factor cannot be used for stratification at randomization, the allocation of the participants with undetectable SARS-CoV-2 in baseline NP swabs randomized to the 2 intervention groups may not be in a 1:1 ratio. If at least 10% of the approximately 276 participants with detectable SARS-CoV-2 in baseline NP swabs are randomized to the MOV group, the study has at least 90% power to demonstrate the superiority of MOV over placebo for participants with undetectable SARS-CoV-2 in baseline NP swabs at an overall one-sided 2.5% alpha-level. The power and sample size calculation for the primary objective were computed using EAST and based on the following assumptions:

- The percentage of participants with undetectable SARS-CoV-2 in baseline NP swabs is assumed to be 80% among the 1376 participants (see Section 4.2.3), resulting in approximately 1100 participants with undetectable SARS-CoV-2 in baseline NP swabs.
- The background secondary attack rate, in the absence of MOV, for participants with undetectable SARS-CoV-2 in baseline NP swabs, is assumed to be ~8% [Regeneron Pharmaceuticals, Inc. 2021].

- MOV is assumed to reduce the background secondary attack rate for participants with undetectable SARS-CoV-2 in baseline NP swabs by 60%, resulting in a secondary attack rate of ~3.2% in the MOV group.

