- A futility interim analysis at 55% information as outlined in Section 9.7. The Haybittle-Peto type adjustment [Haybittle, J. L. 1971] [Peto, R, et al 1976] with a small amount of alpha (α =0.0001) will be applied to this interim analysis.

Some selected power and sample size calculations are presented in Table 7, including the extreme cases where all participants with detectable SARS-CoV-2 in baseline NP swabs are either in the MOV or the placebo group, and some less-extreme scenarios:

- 1. In the scenario where the approximately 276 participants with detectable SARS-CoV-2 in baseline NP swabs are balanced between the 2 intervention groups (allocation ratio of 1), approximately 550 participants with undetectable SARS-CoV-2 in baseline NP swabs would be randomized to each group.
- 2. In the scenario where the approximately 276 participants are all randomized to the MOV group, there would be approximately 412 participants with undetectable SARS-CoV-2 in baseline NP swabs in this group versus approximately 688 in the placebo group, with an allocation ratio (MOV versus placebo) of 0.6.
- 3. In the scenario where the approximately 276 participants are all randomized to the placebo group, there would be approximately 688 participants with undetectable SARS-CoV-2 in baseline NP swabs in the MOV group versus approximately 412 in the placebo group with an allocation ratio of 1.67.
- 4. Two additional scenarios with allocation ratios of 1.5 and 0.85 are also provided.

All scenarios are based on a total sample size of 1100 participants with undetectable SARS-CoV-2 in baseline NP swabs and an overall one-sided, 2.5% alpha-level.

Table 7Power Analysis to Assess the Primary Objective in Participants WithUndetectable SARS-CoV-2 in Baseline NP Swabs; N=1100 Participants, OverallAlpha=0.025, One-sided

Sample Size	Allocation Ratio	Sample Size in MOV	Sample Size in Placebo	Power (%)
1100	1.67	688	412	89
1100	1.5	660	440	90
1100	1	550	550	93
1100	0.85	505	595	94
1100	0.6	412	688	94
MOV=molnupiravir	; NP=nasopharyngeal			

As shown in Table 7, the power in the first scenario (the extreme case where all approximately 276 participants with detectable SARS-CoV-2 in baseline NP swabs are in the placebo group) is approximately 89%. In scenarios where at least 10% of the participants with detectable SARS-CoV-2 in baseline NP swabs are in the MOV group, there is at least 90% power.

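### Table 8 gives stand-alone power for the secondary hypothesis without saying so; with H1 as a gate, the power to establish H2 is about 91–93% at equal allocation (not 95%) and about 90–94% in the third scenario (not >99%)

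*Combined protocol and SAP*

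**What the plan says.** Section 9.8 (Multiplicity), summarised in Section 9.1, sets a fixed sequence. "The secondary hypothesis (H2) will be tested only if H1 is rejected", and "If H1 fails to reach statistical significance, then H2 will not be tested". On the level: "Both tests will be performed at the same one-sided 2.49% alpha-level".

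Section 9.9.1, Table 7, gives H1 power of 93% for 550 MOV and 550 placebo participants with undetectable virus at baseline, and 90% for 660 and 440. The text under the table states at least 90% power "In scenarios where at least 10% of the participants with detectable SARS-CoV-2 in baseline NP swabs are in the MOV group".

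Section 9.9.2, Table 8, gives H2 power for three scenarios of 688 per group:

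| Scenario | Virus-negative (MOV/placebo) | Virus-positive (MOV/placebo) | Stated H2 power |
|---|---|---|---|
| 1 | 500/600 | 188/88 | 24% |
| 2 | 550/550 | 138/138 | 95% |
| 3 | 660/440 | 28/248 | >99% |

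The section carries forward the assumptions of Section 9.9.1 and adds rates for virus-positive participants. It concludes that "the power for the secondary objective analysis is greater than 90% in second and third scenarios". It does not mention the gate, and it does not call its figures stand-alone, marginal or conditional on H1.

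Section 9.6.1 stratifies the H2 test by age, household size and baseline SARS-CoV-2 status.

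**The concern.** Under the gate, H2 can be claimed only in trials where H1 has been rejected. The probability of claiming H2 is therefore P(H1 and H2 both rejected), which is at most P(H1 rejected), whatever the test statistic or the correlation between the tests. Yet Table 8 shows 95% and >99% where Table 7, on the same virus-negative allocations and rates, shows 93% and 90%.

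Someone reading Table 8 as the chance of a formal secondary claim would take scenario 3 as nearly certain. In fact H1 is the binding constraint there, and scenario 3 has the lower H1 power of the two. What is at stake is the accuracy of a reported design property, not a decision rule.

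**Working it through.** **Inputs.** Virus-negative rates are 8% on placebo and 3.2% on MOV (Section 9.9.1: "resulting in a secondary attack rate of ~3.2% in the MOV group"). Virus-positive rates are 40% and 28% (Section 9.9.2). The final level is one-sided 0.0249 (Section 9.8), so z = 1.962. The futility boundary is a risk difference of −0.0049 at 55% information, nonbinding (Section 9.7).

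**Step 1: reproduce Table 7.** Power = Φ(0.048/SE₁ − 1.962), with SE₁ = √(0.08·0.92/n_placebo + 0.032·0.968/n_MOV).
- 550/550: SE₁ = 0.01379; 0.048/SE₁ = 3.481; power 93.6% (stated 93).
- 660/440: SE₁ = 0.01464; 0.048/SE₁ = 3.280; power 90.6% (stated 90).

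All five rows come out as 89.4, 90.6, 93.6, 94.1 and 94.5%, against stated 89, 90, 93, 94 and 94. If the futility boundary is followed, the two rows above become 93.3% and 90.3%. A pooled-variance formula matches only the 550/550 and 505/595 rows.

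**Step 2: reproduce Table 8.** Blend the rates within each group of 688 and compare them without stratification, using unpooled variance.
- Scenario 1: MOV (500·0.032 + 188·0.28)/688 = 9.98%; placebo (600·0.08 + 88·0.40)/688 = 12.09%; power 23.9% (stated 24).
- Scenario 2: MOV (550·0.032 + 138·0.28)/688 = 8.17%; placebo (550·0.08 + 138·0.40)/688 = 14.42%; difference 0.0624, SE₂ = 0.01698; power 95.7% (stated 95).
- Scenario 3: MOV (660·0.032 + 28·0.28)/688 = 4.21%; placebo (440·0.08 + 248·0.40)/688 = 19.53%; power >99.9% (stated >99).

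Table 8 is therefore the stand-alone, unstratified H2 power with the gate left out.

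**Step 3: bounds from the printed figures alone.** Joint power lies between P(H1) + P(H2) − 1 and the smaller of the two. In scenario 2 that is 93 + 95 − 100 = 88% up to about 93%. In scenario 3 it is just above 89% up to about 90%. Both ranges inherit the rounding of the tables.

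**Step 4: joint power, same formula.** The two estimates share the virus-negative participants, so their covariance is (0.08·0.92 + 0.032·0.968)/688 = 0.000152. In scenario 2 the correlation is 0.000152/(0.01379 × 0.01698) = 0.649; in scenario 3 it is 0.613. Bivariate normal probabilities, with trivariate ones when the futility boundary is followed, give:

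| Scenario | H1 | H2 alone | Both | Both, futility followed |
|---|---|---|---|---|
| 1 | 94.2% | 23.9% | 23.9% | 23.9% |
| 2 | 93.6% | 95.7% | 91.1% | 90.9% |
| 3 | 90.6% | >99.9% | 90.6% | 90.3% |

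**Step 5: score-type tests.** One million simulated trials per scenario used pooled-variance tests, with H2 either unstratified or stratified by baseline viral status. H1 was not stratified by age or household size. Without futility stopping:

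| Scenario | H1 | H2 alone, unstratified | Both | H2 alone, stratified | Both |
|---|---|---|---|---|---|
| 1 | 93.9% | 22.2% | 22.2% | 97.3% | 92.7% |
| 2 | 94.2% | 96.8% | 92.6% | 97.8% | 93.2% |
| 3 | 93.8% | 100% | 93.8% | 95.0% | 91.8% |

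Following the futility boundary lowers the joint figures in scenarios 2 and 3 to 92.3% and 92.9%, and to 93.4% and 91.6%. In scenario 1 the stratified joint figure becomes 92.4%.

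**The case against.** The strongest reply is that Table 8 contains no error. Reporting power test by test in a fixed sequence is common, the section speaks of power for a comparison, and Sections 9.1 and 9.8 disclose the gate. Much of this stands: the figures are correct for a stand-alone unstratified test, and only the missing label and the missing joint figure are at fault. A reader might infer an arithmetic mistake or impossible figures. Step 2 does not support that; the conflict arises only when the figures are read as the probability of establishing H2.

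A reader might also infer that the over-90% statement fails in scenario 3 because Table 7 caps it at 90%. That goes too far. The 90 is rounded, the text beside it says at least 90% when at least 10% of virus-positive participants are on MOV (28/276 = 10.1%), and every joint calculation for that scenario stays just above 90%.

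A third inference, that scenario 1 is untouched by the gate, holds only for an unstratified test. Under the stratification in Section 9.6.1 the gate costs about 5 points there (97.3% to 92.7%).

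The consequence is also fairly described as small. Scenario 3 is illustrative: under simple 1:1 allocation the MOV count of virus-positive participants has SD √(276 × 0.25 × 1100/1375) = 7.4, so 28 lies (138 − 28)/7.4, or about 15 SDs, below the expected 138.

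None of this makes 95% or >99% the power under the plan's testing order. Joint power is below both in every calculation.

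**Conclusion.** The point holds as one of labelling and completeness. At equal allocation the stated 95% exceeds the power to establish H2 by about 2 to 4 points. In scenario 3 the stated >99% exceeds it by about 5 to 9 points. The ranges reflect the variance form, stratification by viral status, and whether the nonbinding futility boundary is followed; the direction does not depend on them. All figures rest on the plan's assumed attack rates and treatment effects.

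The stated 24% in scenario 1 is a separate matter. It describes an unstratified test that Section 9.6.1 does not plan. The sample size is justified on H1 and is unaffected, as are type I error control and every decision rule.

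**What to change.** Restate Table 8 and its concluding sentence as the probability that H1 and H2 are both rejected. Compute it with the planned H2 test, stratified as in Section 9.6.1, and state the variance form and whether futility stopping is assumed. If the present figures are kept, label them as stand-alone power for an unstratified comparison, refer to Section 9.8, and print the joint figures beside them.

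The cost is a recalculation and a table edit, with no change to design or conduct. The figures for scenarios 2 and 3 fall slightly; under the planned stratified test, scenario 1 rises from 24% to about 93%.

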4.2.3 Rationale for the Selected Participant Population

Household contacts living with a SARS-CoV-2-infected individual will comprise the participant population in this study. As noted in Section 2.1, household contacts are at elevated risk of developing COVID-19 due to their extended close proximity with this individual who is shedding virus and therefore, are potential candidates for prophylaxis with MOV.

In this study, a household is defined as a unit with shared living space(s) with no more than 10 inhabitants (ie, large communal living arrangements such as dormitories, hostels, barracks, and long-term care facilities do not qualify as households). There is no requirement that the household residents share a familial relationship.

The primary endpoint is analyzed in those without detectable SARS-CoV-2 virus at baseline (ie, the Day 1 NP swab; those with detectable virus prior to randomization are ineligible). Recent data from a study of household prophylaxis with casirivimab and imdevimab [O'Brien, M. P., et al 2021] showed that COVID-19 incidence rates are substantially higher in the population that has detectable virus via PCR at baseline than in the population that does not have detectable virus at baseline. The viral status is not known at the time of randomization due to the duration required for RT-PCR testing. Since randomization cannot therefore be stratified to assure balance between the arms, the 2 populations will be analyzed both separately and together for onset of disease. It is assumed that up to 20% of the enrolled population may have detectable virus at baseline, in consideration of the virus-positive (or viral status unknown) percentage (16.5%) reported by O'Brien [O'Brien, M. P., et al 2021] and a conservative adjustment to 20% based on the higher infectivity of more recently reported viral variants.

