Moreover, a participant without a Day 14 clinical outcome assessment, but assessed as a clinical success through Day 29 will be treated as a clinical success through Day 14. A participant without a Day 29 clinical outcome assessment, but assessed as a clinical failure through Day 14 will be treated as a clinical failure through Day 29. If a participant discontinued from the study prior to the Day 14 or the Day 29 visit, but was assessed as a clinical failure from the COVID-19 Confirmation Visit, then the clinical failure should be carried forward to the Day 14 and/or the Day 29 visit after the COVID-19 Confirmation Visit. All other missing clinical outcome assessments will be imputed as clinical failures.

For the evaluation of the secondary hypothesis, the superiority of MOV compared with placebo with respect to the percentage of participants (regardless of SARS-CoV-2 results in baseline NP swabs) developing COVID-19 by Day 14 will be assessed using the same method in the primary hypothesis, ie, the stratified Miettinen and Nurminen method with CMH weights [Miettinen, O. and Nurminen, M. 1985] (stratified by age and household size as described in Section 6.3.2, and SARS-CoV-2 status in baseline NP swab). The secondary hypothesis will be evaluated by testing the null hypothesis $p_{ts} \ge p_{cs}$ versus the alternative hypothesis $p_{ts} < p_{cs}$, where p_{ts} and p_{cs} refer to event rates (percentages of participants developing COVID-19 by Day 14) in MOV and placebo groups, respectively. The null hypothesis will be rejected if the 1-sided p-value is less than 0.0249 (see Section 9.8 for alpha adjustment) and the superiority of MOV relative to placebo will be concluded for this secondary endpoint.

The efficacy of MOV compared with placebo for the prevention of COVID-19 with respect to the percentage of participants with undetectable SARS-CoV-2 in baseline NP swabs developing COVID-19 through Day 29 will be evaluated. The difference in percentages between treatment groups (MOV minus placebo) and the associated 95% CI will be

MK-4482-013-05 FINAL PROTOCOL

16-OCT-2022

calculated using the stratified Miettinen and Nurminen method with CMH weights [Miettinen, O. and Nurminen, M. 1985] (stratified by age and household size as described in Section 6.3.2).

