For the evaluation of the prevention of viral transmission using MOV compared with placebo through Day 14 among participants with undetectable SARS-CoV-2 in NP swabs at baseline, the percentage of participants in the 2 intervention groups who have positive/detectable SARS-CoV-2 RNA through Day 14 will also be compared using the stratified Miettinen and Nurminen method [Miettinen, O. and Nurminen, M. 1985] (stratified by age and household size as described in Section 6.3.2).

The efficacy of MOV compared with placebo for the prevention of COVID-19 with respect to the percentage of participants with detectable SARS-CoV-2 in baseline NP swabs developing COVID-19 through Day 14 will be evaluated. The difference in percentages between treatment groups (MOV minus placebo) and the associated 95% CI will be calculated using the Miettinen and Nurminen method with CMH weights [Miettinen, O. and Nurminen, M. 1985].

A detailed analysis strategy for key efficacy endpoints is listed in Table 5.

Endpoint/Variable (Description, Time Point)	Primary vs Supportive Approach ^a	Statistical Method	Analysis Population	Missing Data Approach
Primary				
Percentage of participants with undetectable SARS-CoV-2 in baseline NP swabs developing COVID-19 by Day 14	Р	Stratified M&N method with CMH weights ^b	mITT-VN	As described in 9.6.1
Percentage of participants with undetectable SARS-CoV-2 in baseline NP swabs developing COVID-19 by Day 14	S	Stratified M&N method with CMH weights ^b	РР	Observed data only
Secondary				
Percentage of participants (regardless of SARS-CoV-2 results in baseline NP swabs) developing COVID-19 by Day 14	Р	Stratified M&N method with CMH weights ^b	mITT	As described in 9.6.1
Percentage of participants (regardless of SARS-CoV-2 results in baseline NP swabs) developing COVID-19 by Day 14	S	Stratified M&N method with CMH weights ^b	РР	Observed data only

Table 5	Analysis	Strategy	for Kev	Efficacy Endpoin	nts
1 4010 5	1 mary 515	Shategy	101 1109	Lineacy Linapon	110

Endpoint/Variable (Description, Time Point)	Primary vs Supportive Approach ^a	Statistical Method	Analysis Population	Missing Data Approach
Percentage of participants with undetectable SARS-CoV-2 in baseline NP swabs developing COVID-19 by Day 29	р	Stratified M&N method with CMH weights ^b	mITT-VN	As described in 9.6.1
Percentage of participants with undetectable SARS-CoV-2 in baseline NP swabs developing COVID-19 by Day 29	S	Stratified M&N method with CMH weights ^b	РР	Observed data only

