Percentage of participants who develop positive/detectable SARS-CoV-2 through Day 14 among those with undetectable SARS-CoV-2 in NP swabs at baseline	р	Stratified M&N method with CMH weights ^b	mITT-VN	M=C ^c
Percentage of participants who develop positive/detectable SARS-CoV-2 through Day 14 among those with undetectable SARS-CoV-2 in NP swabs at baseline	S	Stratified M&N method with CMH weights ^b	РР	Observed data only
Percentage of participants with detectable SARS-CoV-2 in baseline NP swabs developing COVID-19 by Day 14	р	Stratified M&N method with CMH weights ^b	mITT-VN	As described in 9.6.1
Percentage of participants with detectable SARS-CoV-2 in baseline NP swabs developing COVID-19 by Day 14	S	Stratified M&N method with CMH weights ^b	РР	Observed data only

C=case of COVID-19; CMH=Cochran-Mantel-Haenszel; M=missing; M&N=Miettinen and Nurminen; mITT-VN=modified intent-to-treat population with undetectable SARS-CoV-2 in baseline NP swabs; NP=nasopharyngeal; PP=per-protocol.

^a P=Primary approach; S=Supportive approach.

^b Miettinen and Nurminen method with CMH weights stratified by age and household size.

^c M=C is Missing considered as a case of COVID-19.

Participants in Ukraine who were randomized in FEB 2022 without clinical outcome assessment on Day 14 will be excluded from the efficacy analysis.

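### The strata for the H2 test conflict between Section 9.6.1 and Table 5, and Table 8 gives the power of an unstratified comparison instead of the planned test

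*Combined protocol and SAP*

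**What the plan says.** Section 9.6.1 tests H2 with the Miettinen and Nurminen method and CMH weights, "stratified by age and household size as described in Section 6.3.2, and SARS-CoV-2 status in baseline NP swab". In Table 5 of the same section, the endpoint "Percentage of participants (regardless of SARS-CoV-2 results in baseline NP swabs) developing COVID-19 by Day 14" has two rows, one for the mITT population and one for the Per-Protocol population. Both carry footnote b, which reads "Miettinen and Nurminen method with CMH weights stratified by age and household size". Baseline viral status is missing from it.

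Section 9.8 tests H2 only if H1 is rejected: "Both tests will be performed at the same one-sided 2.49% alpha-level".

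Table 8 in Section 9.9.2 gives H2 power for three splits of the participants with detectable virus at baseline (V+) and undetectable virus (V−). The figures are 24%, 95% and >99%. The text below the table says "There is substantially less power in the first scenario where there is a marked and unfavorable imbalance in randomization", and attributes this to the imbalance "causing the difference in the overall secondary attack rates between the 2 intervention groups to be smaller".

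**The concern.** There are two linked problems.

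1. A test under type I error control should have one prespecified set of strata. Here the text and the table differ on the factor that matters most: the plan assumes a 40% placebo attack rate in V+ participants against 8% in V−. Viral status is unknown at randomization, and Section 4.2.3 says "Since randomization cannot therefore be stratified to assure balance between the arms". Balance on it is left to chance, so it matters whether the analysis adjusts for it.

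2. The reason given for the 24% is that the difference in overall rates shrinks when V+ participants cluster in the MOV arm. That is how a comparison of pooled arm rates behaves. A test stratified by baseline status compares arms within V+ and within V−, so the mechanism largely disappears. If Table 8 was computed without baseline status, it describes a different test from the one in Section 9.6.1, and readers are told that H2 power could collapse when it would not.

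**Working it through.** **Inputs.** Attack rates, placebo v MOV: V− 8% v 3.2% (Section 9.9.1); V+ 40% v 28% (Section 9.9.2). Cell sizes are those of Table 8, with 688 per arm. One-sided alpha is 0.0249 (Section 9.8), critical value 1.962.

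**Step 1: reproduce Table 8 without baseline status.** Mix the two rates within each arm and compare the pooled rates. For row 1:

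- MOV: (500 × 0.032 + 188 × 0.28)/688 = 68.64/688 = 9.98%
- Placebo: (600 × 0.08 + 88 × 0.40)/688 = 83.2/688 = 12.09%
- Difference 0.0212; standard error 0.0169 under both the null and the alternative
- Power = Φ[(0.0212 − 1.962 × 0.0169)/0.0169] = 23.9%

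| Row | V+ MOV / placebo | Pooled rates, MOV v placebo | Unstratified power | Table 8 |
|---|---|---|---|---|
| 1 | 188 / 88 | 9.98% v 12.09% | 23.9% | 24% |
| 2 | 138 / 138 | 8.17% v 14.42% | 95.6% | 95% |
| 3 | 28 / 248 | 4.21% v 19.53% | >99.9% | >99% |

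All three entries match within 1 point.

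**Step 2: the test in Section 9.6.1, stratified by baseline status.** The stratum weight is w = n_t·n_c/(n_t + n_c). The risk differences are 0.048 (V−) and 0.12 (V+). The null variance uses the common rate within each stratum, with the factor N/(N − 1). For row 1:

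- w(V−) = 500 × 600/1100 = 272.7; w(V+) = 188 × 88/276 = 59.9
- Weighted difference = (272.7 × 0.048 + 59.9 × 0.12)/332.7 = 0.0610
- Standard error 0.0159 (null) and 0.0157 (alternative)
- Power = Φ[(0.0610 − 1.962 × 0.0159)/0.0157] = 97.1%

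| Row | Weighted difference | Power, formula | Power, simulation | Table 8 |
|---|---|---|---|---|
| 1 | 0.0610 | 97.1% | 97.3% | 24% |
| 2 | 0.0624 | 97.6% | 97.8% | 95% |
| 3 | 0.0543 | 94.5% | 95.0% | >99% |

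For the planned test, Table 8 is about 73 points too low in row 1, 2 to 3 points too low in row 2 and about 5 points too high in row 3.

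**Step 3: how likely the splits are.** Under 1:1 randomization the number of the 276 V+ participants in the MOV arm is hypergeometric, with mean 138 and SD 7.4. The central 95% range is 123 to 153. A split at least as extreme as row 1 has probability about 9 × 10⁻¹², and as row 3 about 4 × 10⁻⁵⁵.

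**Step 4: what the choice of strata changes.** The unstratified test stands in here for the footnote b analysis, because the plan gives no rates by age or household size.

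| Case | Unstratified power | Unstratified type I error | Stratified power | Stratified type I error |
|---|---|---|---|---|
| Averaged over randomization | 95.6% | 2.5% | 97.5% | 2.5% |
| 123 V+ in MOV, fixed | 99.5% | 9.4% | about 97.5% | about 2.5% |
| 153 V+ in MOV, fixed | 85.4% | 0.2% | about 97.5% | about 2.5% |

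With the row 3 split and no drug effect, the unstratified test rejects in more than 99.9% of simulated trials. The >99% in that row therefore mainly reflects confounding by baseline status.

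**The case against.** The strongest reply is that little depends on Table 8. Its arithmetic is correct for the comparison it makes, and powering a stratified test by an unstratified approximation is common. Table 7 also reproduces without strata (89.4, 90.6, 93.6, 94.1 and 94.5 against 89, 90, 93, 94 and 94), although H1 is stratified. The 73-point gap is confined to a row that randomization will not produce. In the realistic row the stated 95% is slightly conservative, and sample size is driven by H1. The footnote is shared by every row of Table 5, so the H2-specific text in Section 9.6.1 is probably what was intended. Results will also be shown separately for V− and V+, so an imbalance would be visible.

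Most of this stands, and it limits the consequences. It does not remove the point. Section 9.9.2 does not label its figures as an approximation, and states the loss of power in row 1 as a property of the H2 analysis. Nor is the approximation uniformly conservative, since row 3 is overstated. It is tolerable for Table 7 because that population contains only V− participants, so baseline viral status cannot distort it; H2 mixes two groups whose attack rates differ fivefold. Probable intent does not settle the strata of a confirmatory test when the analysis table says otherwise.

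It is also fair that the unstratified figures are only a proxy for footnote b, and that randomization balances viral status on average even though it cannot be stratified on it.

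**Conclusion.** Both parts hold. Section 9.6.1 and Table 5 specify different strata for the H2 test, and nothing else in the documents resolves the difference. Table 8 and the sentence beneath it describe an unstratified comparison. The test in Section 9.6.1 has about 97%, 98% and 95% power in the three rows, so both the warning of low power and the ranking of the rows are wrong for it.

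This is not an error-rate failure on average. Omitting baseline status would cost about 2 points of power. It would also leave the H2 result sensitive to ordinary chance imbalance, with conditional type I error between about 9.4% and 0.2% over the 95% range of splits.

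The figures rest on the plan's assumed rates holding across age and household-size strata. They ignore household correlation, missing-as-case imputation, the H1 gate and the non-binding futility look. None of these would plausibly account for a 73-point gap. The matter should be fixed; it does not threaten the design.

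**What to change.** 1. Give the two H2 rows of Table 5 their own footnote naming three strata: age, household size and baseline SARS-CoV-2 status, as in Section 9.6.1.
2. Recompute Table 8 for that test, with the sponsor confirming the values in its own software (expected about 97%, 98% and 95%). Otherwise, label the present figures as an unstratified approximation.
3. Delete the sentence on reduced power in the first scenario, or state that it applies only to an unstratified comparison.
4. Optionally, replace rows 1 and 3 with splits that 1:1 randomization can produce, such as 123/153 and 153/123 V+ participants. Stratified power is about 97.5% in both.

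The cost is one footnote, three table cells and one sentence. Sample size, alpha and conduct do not change.
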